16.2.	INTRAOPERATIVE OCULAR ADVERSE EVENTS	.19

16.3.	POSTOPERATIVE OCULAR ADVERSE EVENTS	19
17.	ADVERSE EXPERIENCE AND COMPLICATION REPORTING	21
18.	CONCOMITANT MEDICATIONS/THERAPY	22
19.	DATA COLLECTION	22
19.1.	DEVICE ACCOUNTABILITY	22
19.2.	PROTOCOL DEVIATIONS	
19.3.	STUDY COMPLETION PROCEDURES	22
	SUBJECT COMPLETION	
19.3.2.	SUBJECT TERMINATION	22
19.3.3.	SUBJECT DISCONTINUATION	
20.	DATA REPORTING	23
21.	RECORDING OF DATA AND RETENTION OF DOCUMENTS	23
22.	STUDY MONITORING	24
22.1.	REMOTE STUDY MONITORING – COVID-19	24
23.	CONFIDENTIALITY	
24.	APPENDICES	26

PROTOCOL IOPCL AMD-20

Early Feasibility Study to Evaluate the Safety and Effectiveness of the IOPCL AMD MAG for Secondary Implantation in the Capsular Bag to Improve Near Vision in Subjects with Age-Related Macular Degeneration after Cataract Surgery

Sponsor: OnPoint Vision Inc.

[name]

[contact]

Medical Monitor: TBD

SUMMARY OF PROTOCOL REVISIONS

Revision Date	Description of Protocol Revision(s)
8/30/2021	Initial release
10/26/2021	 Addition of Alcon SA60WF as an acceptable model for the previously implanted PCIOL Update figures with AMD MAG IOPCL Clarification within the Surgical Instructions for Use: timing of corneal markings (prior to creation of incisions) change in the incision size of the self-sealing incision from 2.5 mm to 2.75 mm use of viscoelastic to hydrolytically lift the leaflet to receive the trailing haptics use of viscoelastic on the surface center of the IOPCL to aid with proper closure of the cartridge flap complete clearing of viscoelastic at the close of the IOPCL procedure use of a miotic to reduce the pupil size at the close of the IOPCL procedure other minor clarifications other minor clarifications
05/23/2022	4. Revised central magnification power from 11.0 diopters to 10.0.
06/03/2022	 Addition of safety endpoints: a. Preservation of BCNVA - Proportion of eyes (<5%) that lose two or more lines of BCNVA (≥10 letters on the Sloan Near Vision Chart at 14 cm) at 12 months from baseline b. Assessment of absolute tilt of the IOPCL-AMD-MAG and the PCIOL 2. Clarification of definition of decentration 3. Addition of secondary effectiveness endpoint

	Addition of eligibility criterion requiring subjects to have experienced and failed high-magnification refractive correction
	alternatives to the AMD-MAG IOPCL
	7. Addition of eligibility criteria excluding subjects with capsular
	instability and subjects with an anterior capsule defect caused by
	Nd:YAG capsulotomy
	8. Clarification of testing distance for UCDVA and BCDVA
	9. Clarification that assessment of IOPCL location should be performed
	after dilation
	10. Addition of measurement of reading speed as a clinical assessment to
	assess improvement in reading speed
	11. Addition of assessment of capsular stability preoperatively,
	intraoperatively and postoperatively
	12. Revisions to surgical procedure including stopping rules
	13. References of "IOL" revised to "PCIOL" throughout document
	14. Minor clarifications
12/XX/2022	Revision from "contact" to "capsular" for definition of IOPCL
	2. Correction to definition of a centered IOPCL AMD-MAG (i.e.,
	maximum distance of uniform exposed area of the PCIOL outside of
	the IOPCL changed from "1.75 mm" to "0.75 mm")
	3. Clarification to safety endpoint of incidence of adverse events based
	on ISO 11979-7 Grid and non-ISO-Grid
	4. Addition of secondary surgical intervention safety endpoint
	5. Addition of secondary effectiveness endpoints for UCNVA and
	BCNVA
	6. Removal of inclusion criterion #4 following confirmation that
	Nd:YAG capsulotomy can be performed on an acrylic IOPCL.
	7. Modifications to surgical technique 8. Revised exclusion criterion #4
	Minor clarifications

Protocol IOPCL AMD-20

Early Feasibility Study to Evaluate the Safety and Effectiveness of the IOPCL AMD-MAG for Secondary Implantation in the Capsular Bag to Improve Near Vision in Subjects with Age-Related Macular Degeneration after Cataract Surgery

1. STUDY PURPOSE

To determine if the intraocular pseudophakic capsular lens (IOPCL), referred to as the IOPCL AMD-MAG, improves uncorrected near vision in subjects with age related macular degeneration when previously implanted with a Alcon SN60WF, SA60AT, or SA60WF monofocal posterior chamber intraocular lens (PCIOL) and to confirm its positional stability and adherence relative to the PCIOL.

2. STUDY DESIGN

This will be a 12-month study, in which a maximum of 10 pseudophakic subjects from three clinical sites with a diagnosis of age-related macular degeneration will be enrolled. In order to minimize bias, investigators recruited for this study will not have prior surgical experience with the IOPCL.

This study is being conducted in accordance with 21 CFR Parts 50, 54, 56 and 812.42 (U.S.C 282(j)). ISO 14155 Clinical investigation of Medical Devices for Human Subjects, ISO 11979-7, and the ethical principles laid down in the Declaration of Helsinki.

3. INTRODUCTION AND RATIONALE

The IOPCL (intraocular pseudophakic contact lens) AMD-MAG consists of a 4.5 mm diameter concave-convex optic with three opposing haptic straps, or tabs. The central 1.8 mm of the anterior surface of the optic has a power of 10 diopters. The haptic straps are designed to enter and rest within three channels created under the anterior leaflet of the capsular bag. Each channel is created with a Capsule Separator spatula. Each haptic strap or tab has a small pawl, or ridge on the bottom that is used to catch and lock on to the PCIOL optic edge. This pawl aids in both centering the IOPCL AMD -MAG on the PCIOL optic as well as allowing the haptic strap to stay securely seated while contained under the surface tension of the anterior leaflet of the capsular bag. The lens is designed to improve near vision of the AMD subject by providing magnification of 10 diopters in the central 1.8mm zone of the lens optic to improve near vision.

4. STUDY OBJECTIVE

The primary objective of this study is to determine the stability of the IOPCL-AMD-MAG to successfully adhere to a pseudophakic intraocular lens without rotation or slippage.

The secondary objective of this study is to determine if the IOPCL-AMD-MAG can improve uncorrected near visual acuity in subjects previously implanted with an Alcon SN60WF or SA60AT monofocal intraocular lens.

4.1. Safety Endpoints

- Preservation of BCDVA Proportion of eyes (< 5%) that lose two or more lines of BCDVA (≥10 letters on the ETDRS chart) at 12 months from baseline.
- Preservation of BCNVA Proportion of eyes (<5%) that lose two or more lines of BCNVA
 (≥10 letters on the Sloan Near Vision Chart at 14 cm) at 12 months from baseline.
- Incidence of secondary surgical intervention (SSI).
- Successful delivery of the IOPCL AMD-MAG as determined at all postoperative scheduled visits starting at 7-14 days post-operative.
 - No capsular tear
 - No visible damage to either the PCIOL or the IOPCL AMD MAG
 - o Uniform leaflet coverage of all IOPCL AMD MAG haptic tabs
- Long-term adherence and positional stability
 - O Gap: Minimal change in uniformity of the gap between consecutive scheduled visits at 1-2 months and later as determined by UBM measurements. Minimal change is defined as +/- 10 microns between visits is established and maintained using UBM imaging.
 - o Tilt:
- Tilt of the PCIOL as determined at all post-operative scheduled visits starting at 30-60 days post-operative. Minimal tilt of the PCIOL confirmed via penlight examination and defined as ≤ 10 degrees between the postoperative tilt of the PCIOL and the pre-operative tilt of the PCIOL.
- Tilt of the IOPCL AMD-MAG as determined at all post-operative scheduled visits starting at 30-60 days post-operative. Minimal tilt of the IOPCL AMD-MAG (using the PCIOL as a reference point) confirmed via penlight examination and defined as ≤ 10 degrees between the post-operative tilt of the. PCIOL and the postoperative tilt of the IOPCL AMD-MAG.
- O Decentration: Decentration as determined at all post-operative scheduled visits starting at 7-14 days post-operative. Centration of the IOPCL AMD-MAG (using the PCIOL as a reference point) confirmed during slit lamp examination and defined as uniform exposed area of the PCIOL outside of the IOPCL AMD-MAG at the vertical and horizontal meridians between ≥ 0.25 mm and ≤ 0.75 mm.
- Counts and percentages for incidence of cumulative and persistent intraoperative and post-operative adverse events
- Counts and percentages for incidence of secondary surgical interventions (e.g., removal
 of interlenticular opacity, repositioning of IOPCL, explant of IOPCL, repositioning of
 PCIOL) (excluding Nd:YAG treatments for PCO).

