the edge of the underlying PCIOL. Confirm the capsule is stable by applying gentle pressure to all three seated haptic. If capsular stability is not confirmed, the IOPCL AMD-MAG should be removed (refer to Section 12.1.7 for removal instructions). Once stability is confirmed, perform thorough irrigation/aspiration of OVD and any displaced cortical material.

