- IOPCL Location (following dilation): 1-2 days, 7-14 days, 30-60 days, 120-180 days, 330-420 days, Interim
- Manifest Refraction: Preoperative, 7-14 days, 30-60 days, 120-180 days, 330-420 days, Interim
 - Post-removal, 7-14 days, 30-60 days, 120-180 days, 330-420 days, Interim
- Add Power: Pre-Operative, 7-14 days, 30-60 days, 120-180 days, 330-420 days, Interim.
 - Post-removal, 7-14 days, 30-60 days, 120-180 days, 330-420 days, Interim
- BCDVA: Best Corrected Distance Visual Acuity (at 6m) Preoperative, 7-14 days, 30-60 days, 120-18 days, 330-420 days, Interim
 - Post-removal, 7-14 days, 30-60 days, 120-180 days, 330-420 days, Interim
- BCNVA: Best Corrected Near Visual Acuity (at 30 cm (preoperatively); 14 cm (postoperatively) and preferred reading distance (preoperatively and postoperatively)) Pre-Operative, 7-14 days, 30-60 days, 120-180 days, 330-420 days, Interim.
 - Post-removal, 7-14 days, 30-60 days, 120-180 days, 330-420 days, Interim

- UCDVA: Uncorrected Distance Visual Acuity (at 6m)— Preoperative, 7-14 days, 30-60 days, 120-180 days, 330-420 days.
 - Post-removal, 7-14 days, 30-60 days, 120-180 days, 330-420 days. Interim
- UCNVA: Uncorrected Near Visual Acuity (at 14 cm and preferred reading distance) –
 Preoperative, 7-14 days, 30-60 days, 120-180 days, 330-420 days
 - Post-removal, 7-14 days, 30-60 days, 120-180 days, 330-420 days, Interim
- Central Visual Field (Amsler Grid): Preoperative
- Reading Speed (Smith-Kettlewell testing at 40 cm): Preoperative, 7-14 days, 30-60 days, 120-180 days, 330-420 days
 - Post-removal, 7-14 days, 30-60 days, 120-180 days, 330-420 days, Interim
- Contrast Sensitivity (Mesopic): Preoperative, 7-14 days, 30-60 days, 120-180 days, 330-420 days
 - Post-removal, 7-14 days, 30-60 days, 120-180 days, 330-420 days, Interim
- Slit Lamp Examination: Preoperative, 1-2 days, 7-14 days, 30-60 days, 120-180 days, 330-420 days, Interim.
 - Post-removal, 1-2 days, 7-14 days, 30-60 days, 120-180 days, 330-420 days, Interim
- Gonioscopy: 7-14 days, 30-60 days, 120-180 days, 330-420 days, Interim
 - Post-removal, 7-14 days, 30-60 days, 120-180 days, 330-420 days, Interim
- Intraocular Pressure: Preoperative, 1-2 days, 7-14 days, 30-60 days, 120-180 days, 330-420 days, Interim
 - Post-removal, 1-2 days, 7-14 days, 30-60 days, 120-180 days, 330-420 days, Interim
- Dilated Fundoscopy: Preoperative, 7-14 days, 30-60 days, 120-180 days, 330-420 days, Interim

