# 3.2 Safety Endpoints

• Preservation of Best Corrected Distance Visual Acuity (BCDVA)

The preservation of BCDVA is defined as proportion of eyes (< 5%) that lose two or more lines (≥10 letters) of BCDVA at 12 months from baseline.

• Preservation of Best Corrected Near Visual Acuity (BCNVA)

Proportion of eyes (<5%) that lose two or more lines of BCNVA (≥10 letters on the Sloan Near Vision Chart at 14 cm) at 12 months from baseline.

- Incidence of secondary surgical intervention (SSI)
- Successful Delivery of the IOPCL as determined as all postoperative scheduled visits starting at 7-14 days postoperative.

The successful delivery of the IOPCL is defined as no capsular tear, no visible damage to either the IOL or IOPCL, and uniform leaflet coverage of all IOPCL haptic tabs.

• Long-term Adherence and Positional Stability

The long-term adherence and positional stability is defined as 1) minimal change in uniformity of the gap between consecutive scheduled visits at 1-2 months and later as determined by UBM imaging (where minimal change is defined as +/- 10 microns between visits established and maintained using UBM imaging).

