## 5 ANALYSIS POPULATIONS

The analyses will include the data of all study eyes where implantation of IOPCL was attempted and/or successful.

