# 7.5.4 Successful Delivery of the IOPCL

The analysis of this clinical outcome will be based on the observed data of IOPCL AMD-MAG IOPCL. The number and percent of eyes with successful delivery of the IOPCL will be reported.

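### Successful delivery is read only from the 7-14 day visit, on observed data and with no stated denominator, so operative and early failures can fall out of the rate and bias it upward

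*Protocol*

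**What the plan says.** **Timing.** Protocol 4.1 makes the endpoint "Successful delivery of the IOPCL AMD-MAG as determined at all postoperative scheduled visits starting at 7-14 days post-operative". SAP 3.2 says the same: "Successful Delivery of the IOPCL as determined as all postoperative scheduled visits starting at 7-14 days postoperative". Surgery and the 1-2 day visit (Form 1) are outside it.

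**Criteria.** SAP 3.2: "The successful delivery of the IOPCL is defined as no capsular tear, no visible damage to either the IOL or IOPCL, and uniform leaflet coverage". Coverage here refers to each haptic tab. Completed implantation is not itself a criterion.

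**Analysis.** SAP 7.5.4 works from observed data and says only that "The number and percent of eyes with successful delivery of the IOPCL will be reported". SAP 6.5 uses available data without imputation. SAP 7.5 refers to a safety population that SAP 5 does not define separately. SAP 5 itself says: "The analyses will include the data of all study eyes where implantation of IOPCL was attempted and/or successful".

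**Failure before Form 2.** Protocol 12.1.2 provides for aborting the procedure when the lens/bag complex is too mobile. Protocol 12.1.4 adds: "If capsular stability is not confirmed, the IOPCL AMD-MAG should be removed". Protocol 16.2 lists failure to implant as an intraoperative adverse event. Protocol 16.3 lists IOPCL exchange, repositioning and removal as examples of SSI, with no earliest date.

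**Early examinations.** Protocol 15 schedules "IOPCL Location (following dilation): 1-2 days, 7-14 days, 30-60 days, 120-180 days, 330-420 days, Interim", together with IOPCL location at surgery, slit lamp at 1-2 days, and adverse events at both. The delivery endpoint uses none of these.

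**The concern.** Delivery is largely an operative event. A capsular tear or damage to a lens can arise while the IOPCL is being injected and seated; Protocol 12.1.4 itself warns that haptics can be torn during injection. Yet the endpoint is first read a week or more later, on whatever can then be observed.

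Two kinds of eye are affected. One has no IOPCL at Form 2, because implantation was aborted or failed or the lens was removed. Tab coverage cannot be seen in that eye, and no rule says whether it is a failure or missing. The other had its first lens damaged and exchanged before Form 2. The replacement lens can meet all three criteria, and nothing in the definition looks back.

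If both are handled in the favourable way, the percentage describes eyes that hold a well-seated IOPCL at least a week after surgery, not eyes in which delivery was tried. Protocol 2 recruits investigators with no prior surgical experience of this lens, so early failures are plausible, and with at most 10 eyes each one moves the rate by about 10 points.

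**Working it through.** The documents state no delivery rate, target, alpha or power, so there is no figure to reproduce. The check is how far the rate can move under the readings that the SAP leaves open.

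**Inputs.** n = 10 attempted eyes, the cap in SAP 6.2. k = eyes with no IOPCL at Form 2; the documents give no value, so k = 0 to 3 is assumed. f = eyes that fail a criterion at a later visit, taken as 0 or 1.

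**Formulas.** With s = n − k − f successes:
- eyes without a lens counted as failures: s / n
- eyes without a lens dropped as not observed: s / (n − k)

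**Results with f = 0** (exact Clopper-Pearson 95% limits):

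| k | Counted as failures | Dropped | Gap (points) |
|---|---|---|---|
| 0 | 10/10 = 100% | 10/10 = 100% | 0 |
| 1 | 9/10 = 90% (55.5 to 99.7) | 9/9 = 100% (lower limit 66.4) | 10 |
| 2 | 8/10 = 80% (44.4 to 97.5) | 8/8 = 100% (lower limit 63.1) | 20 |
| 3 | 7/10 = 70% (34.8 to 93.3) | 7/7 = 100% (lower limit 59.0) | 30 |

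**Results with f = 1.** For k = 1, 8/9 − 8/10 = 8.9 points; for k = 2, 7/8 − 7/10 = 17.5; for k = 3, 6/7 − 6/10 = 25.7. Later failures narrow the gap but do not close it.

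**Early exchange.** This route does not depend on the denominator. If one of 10 eyes has a damaged lens exchanged before Form 2 and all eyes pass afterwards, the rate is 10/10 = 100%. Counting that eye as a failure gives 9/10 = 90%.

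**How likely is k ≥ 1?** With early-failure probability p per eye, P(k ≥ 1) = 1 − (1 − p)^10. For assumed p of 5%, 10% and 20%, this is 40%, 65% and 89%.

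**Which reading does the SAP support?** For dropping: SAP 7.5.4 and 6.5 use observed data without imputation, coverage is unobservable without a lens, and SAP 6.4 counts postoperative days from the lens implantation date, which an aborted eye does not have. For counting: SAP 5 keeps attempted eyes in the analyses. No section settles it.

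**The case against.** The strongest case against is that SAP 5 covers "all study eyes where implantation of IOPCL was attempted and/or successful" and no section names a narrower denominator for delivery. On that reading a failed attempt stays in the denominator and the bias from dropped eyes is zero. This stands as far as it goes: dropping is a possible reading, not a stated rule. But SAP 5 includes the data of those eyes; it does not say how an eye with no observable coverage is classified.

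A reader might infer that every eye with failed delivery never reaches the assessment, so that the rate is necessarily too high. The documents do not support that. An eye that keeps its lens with a tear, damage or poor coverage is still examined at 7-14 days, and a removed eye has its own follow-up schedule (Protocol 14.1).

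The events would not be concealed either. Failure to implant and capsular rupture are listed adverse events, summarised intraoperatively, by visit and cumulatively (SAP 7.5.6), and SAP 7.5.3 gives a line listing of each SSI. No threshold or test depends on the delivery rate. This limits the consequence, but those tables do not correct the percentage reported for the endpoint.

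Finally, if the criteria must hold at every visit, late loss of coverage pulls the rate down. That is fair, and SAP 7.5.4 does not say how visits combine. It is a further gap, and it does not cancel the upward routes.

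**Conclusion.** The concern holds as a possible upward bias, not a certain one. The timing rule leaves the operative event out of the endpoint, and SAP 7.5.4 does not state the denominator, the status of eyes without an IOPCL, or how visits combine. With 10 attempted eyes and no later failures, one dropped eye turns 90% into 100% and two turn 80% into 100%. An early exchange scored as a success adds 10 points per eye, whatever rule is used for eyes without a lens when no other eye is lost. With no early failure there is no bias. The numbers of affected eyes are assumptions. Because the analysis is descriptive and the events are tabulated elsewhere, what is at stake is the accuracy of one named safety endpoint, not a pass/fail decision.

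**What to change.** 1. In SAP 7.5.4, make all eyes with attempted implantation (SAP 5) the denominator.
2. In Protocol 4.1, SAP 3.2 and SAP 7.5.4, keep the existing criteria from 7-14 days. Also count an eye as not successfully delivered if there was failure to implant, removal or exchange of the IOPCL before Form 2, or a capsular tear or lens damage recorded at the operative or 1-2 day visit.
3. State whether the criteria must be met at every scheduled visit.
4. List separately the eyes aborted before the lens was inserted and those repositioned before Form 2. SAP 5 does not say whether the former count as attempted, and whether early repositioning is a delivery failure is a matter of judgement. A listing lets the reader see the rate either way.

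**Cost.** Wording in three sections and no new visit. The reported rate may be slightly less favourable. The schedule in Protocol 15 has no specific item for lens damage at surgery or at 1-2 days, so the operative and Form 1 CRFs should be checked to confirm that they record tear and lens damage.

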15. CLINICAL ASSESSMENTS

All parameters will be recorded for both eyes at baseline (pre-operative). Measurements will be recorded for the study eye at postoperative and post-removal visits. See Appendix 2A schedule of visits (pre- and post-operative visits) and Appendix 2B (post-removal visits). See Appendix 3 for clinical assessment instructions.

Order of Clinical Assessments:

- Mesopic contrast sensitivity testing should be performed prior to the slit lamp examination
 and before any visual acuity testing that requires bright light directed at the subject (i.e., a
 reading lamp shined directly over the subject's shoulder onto the reading card).
- Confirmation of IOPCL location should be performed after the study eye is dilated.

Study sites are expected to implement COVID-19 pandemic safety measures in accordance with their local, state, and CDC health guidelines to ensure the health and well-being of the subjects and study staff who come in contact with the subjects.

Clinical Assessments and Timepoints

- Inclusion/exclusion criteria: Preoperative
- Medical history: Preoperative
- External magnifier usage: Preoperative, 30-60 days, 120-180 days, 330-420 days. Interim
 - Post-removal, 30-60 days, 120-180 days, 330-420 days, Interim
- Demographics: Preoperative
- Patient Informed Consent: Preoperative
- Capsulorhexis Size at the time of PCIOL surgery: Preoperative
- Position of PCIOL Haptics and Planned IOPCL Incision Location: Preoperative
- Axial Length: Preoperative
- Keratometry: Preoperative

- Mesopic and Photopic Pupil size measured by Pupillometer: Preoperative.
- Pseudophakic PCIOL power with make and model number: Preoperative.
- Simulation of expected outcome (3.0D lens over manifest refraction at 30cm and 7.0D lens over manifest refraction, at 14cm and preferred distance): Preoperative.
- Ocular Dominance: Preoperative
- Optical Coherence Tomography: Preoperative, 30-60 days, 120-180 days, 330-420 days.
 Interim
 - Post-removal, 30-60 days, 120-180 days, 330-420 days, Interim
- Capsular Stability: Preoperative, Operative, 7-14 days, 30-60 days, 120-180 days, 330-420 days, Interim
 - Post-removal, 7-14 days, 30-60 days, 120-180 days, 330-420 days, Interim
- Spatial Visualization between the PCIOL and IOPCL Using UBM: 30-60 days, 120-180 days, 330-420 days, Interim.
- Recording of the IOPCL Surgical Procedure: Operative
- IOPCL Location and Confirmation of Incision Location: Operative

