# 7.5.5 Long-term Adherence and Positional Stability

The analysis of this clinical outcome will be based on the observed data of IOPCL AMD-MAG IOPCL. The number and percent of eyes with established and maintained central spacing as determined by UBM imaging between the IOPCL and IOL will be reported. The number and percent of eyes reporting decentration of the IOPCL or tilt of the PCIOL and/or IOPCL will be reported.

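### Gap stability is tested only from one scheduled visit to the next, so a net change of up to 20 microns between Form 3 and Form 5 can pass a 10-micron limit

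*Protocol*

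**What the plan says.** Protocol 4.1, under long-term adherence and positional stability, sets the gap criterion as "Gap: Minimal change in uniformity of the gap between consecutive scheduled visits at 1-2 months and later as determined by UBM measurements". The limit follows: "Minimal change is defined as +/- 10 microns between visits is established and maintained using UBM imaging". SAP 3.2 uses the same comparison, "minimal change in uniformity of the gap between consecutive scheduled visits at 1-2 months and later", and the same 10 microns.

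Protocol 15 schedules the imaging: "Spatial Visualization between the PCIOL and IOPCL Using UBM: 30-60 days, 120-180 days, 330-420 days, Interim". The three scheduled visits are Forms 3, 4 and 5; nothing is scheduled before 30 days.

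SAP 7.5.5 describes the output: "The number and percent of eyes with established and maintained central spacing as determined by UBM imaging between the IOPCL and IOL will be reported". It gives no reference visit and no summary of the change in microns. SAP 6.5 says that analyses use available data without imputation. It does not say what happens to a visit-to-visit comparison when one of the two visits is missing.

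The neighbouring criteria in Protocol 4.1 are built differently. PCIOL tilt is compared with its preoperative value, and centration must lie in a fixed band of 0.25 to 0.75 mm.

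**The concern.** The primary objective in Protocol 4 and SAP 2 is stable adherence of the device to the existing lens, and the gap is the UBM-based criterion for it. The reference for that criterion slides: Form 4 is compared with Form 3, and Form 5 with Form 4. Two moderate changes in the same direction can each pass although their sum exceeds the limit. The planned output is a count of eyes, so nothing in SAP 7.5.5 would bring the accumulated change to light.

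The second weakness is attendance. The rule needs Form 4 for both of its comparisons, and the documents do not say how to judge an eye without it. With so few eyes, the reported percentage could turn on a decision taken after the data are seen.

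**Working it through.** **Inputs.** Limit L = 10 microns (Protocol 4.1, SAP 3.2). Scheduled UBM readings G3, G4, G5 at Forms 3, 4 and 5 (Protocol 15). At most 10 eyes (SAP 6.2). The plan reports no calculated figure for this endpoint, so there is none to reproduce.

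**Step 1: what the rule bounds.** Current rule: |G4 − G3| ≤ 10 and |G5 − G4| ≤ 10. Since G5 − G3 = (G4 − G3) + (G5 − G4), the largest net change that passes is (3 − 1) × 10 = 20 microns.

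**Step 2: example paths**, in microns relative to Form 3. With Form 4 missing there are two possible readings. Either Forms 3 and 5 become the consecutive pair (attended-visit reading), or only adjacent scheduled visits count (adjacent-visit reading).

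| Path (G3, G4, G5) | All visits, current rule | Form 4 missing, attended-visit | Form 4 missing, adjacent-visit | All visits, current rule plus Form 3 limit |
|---|---|---|---|---|
| 0, 5, 10 | pass | pass | not evaluable | pass |
| 0, 6, 12 | pass | fail | not evaluable | fail |
| 0, 8, 16 | pass | fail | not evaluable | fail |
| 0, 10, 20 | pass | fail | not evaluable | fail |
| 0, 11, 22 | fail | fail | not evaluable | fail |
| 0, 12, 0 | fail | pass | not evaluable | fail |

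Across all whole-micron paths, 441 pass the current rule with full data. Of these, 110 have a net change above 10 microns, so they fail without Form 4 on the attended-visit reading. This counts paths; it is not a probability. The last row shows the verdict going the other way.

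**Step 3: why both checks are needed.** Limiting change from Form 3 alone caps |G5 − G3| at 10, but still passes 0, +10, −10, a swing of 20 microns between Forms 4 and 5. Both checks together mean that the maximum minus the minimum of the three readings is at most 10.

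**Step 4: with measurement error.** The documents give no UBM reading error. Assume independent normal error with standard deviation s at each visit, and true means 0, d, 2d. Take d = 8 (16 microns of drift) or d = 0 (stable). Each setting used at least 400,000 simulated eyes, for a Monte Carlo standard error of at most √(0.25/400,000) ≈ 0.0008.

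| Assumed s (microns) | 16-micron drift: current rule | 16-micron drift: with Form 3 limit | Stable: current rule | Stable: with Form 3 limit |
|---|---|---|---|---|
| 2 | 54% | 2% | 99.9% | 99.9% |
| 4 | 34% | 12% | 86% | 82% |
| 8 | 23% | 16% | 42% | 35% |

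**Step 5: missing Form 4, attended-visit reading.** The pass probability is Φ((10 − 2d)/(s√2)) − Φ((−10 − 2d)/(s√2)). For s = 4, s√2 = 5.66. A stable eye gives 2Φ(1.77) − 1 = 92%, against 86% with full attendance. A 16-micron drift gives Φ(−1.06) − Φ(−4.60) = 14%, against 34% with full attendance. Missing the visit helps the stable eye and hurts the drifting one.

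**Step 6: weight of one eye.** 1/10 = 10 percentage points at full enrolment, and more with fewer evaluable eyes.

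**The case against.** The best case for leaving the rule alone has four parts.

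- The study is descriptive, has at most 10 eyes, and sets no success proportion for the gap. All three readings are collected, so the Form 3 to Form 5 change could be reported without redefining anything. This limits the consequence. However, SAP 3.3 only lists UBM spacing as an outcome, and SAP 7 plans no summary of it beyond the count in 7.5.5.
- Cumulative movement is not judged by the gap alone. Tilt and centration have their own limits, unseated tabs and malposition are listed adverse events (Protocol 16.3), and lens location is checked after dilation at each postoperative visit. This stands. It does not make the gap criterion measure long-term change.
- The wording about spacing being established and maintained might imply a reference level. No section sets one.
- With a large reading error the added limit separates drift from stability poorly and fails more stable eyes. This stands too, as the s = 8 row shows.

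Three stronger readings are tempting, and the documents do not support them. A reader might infer that missing Form 4 turns a pass into a fail. The rule speaks of scheduled visits, a missed Form 4 is still scheduled, and the eye may equally be not evaluable. A reader might infer that full attenders get an easier test. That is false for a stable eye (86% against 92% at s = 4) and for the path 0, 12, 0. A reader might take steady drift to be the expected sign of a tab loosening. The documents do not say so, and the arithmetic does not need it.

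**Conclusion.** The point holds as a weakness in the endpoint definition. With three scheduled UBM visits, an eye can be counted as maintained after a net change of up to 20 microns from Form 3 to Form 5, twice the stated limit. This follows from the wording and the visit schedule alone.

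The missed-visit problem is one of silence. An eye with a net change above 10 and up to 20 microns goes from pass to fail on one reading and from pass to not evaluable on the other, and some paths that reverse direction go from fail to pass.

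The simulated percentages rest on an assumed reading error and show direction and range only. It would also go too far to say that the lens itself moves 20 microns. The endpoint definitions refer to "minimal change in uniformity of the gap between consecutive scheduled visits at 1-2 months and later as determined by UBM imaging", whereas the analysis counts the "number and percent of eyes with established and maintained central spacing as determined by UBM imaging", so the measured quantity is not settled. The change is worth making before the data are analysed; it does not put the feasibility study as a whole in doubt.

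**What to change.** - **Protocol 4.1 and SAP 3.2:** keep the visit-to-visit check and add that the change from the Form 3 reading must also lie within 10 microns either way at each later scheduled UBM visit. The sponsor's limit is unchanged.
- **SAP 7.5.5, reporting:** give the number and percent of eyes meeting the full criterion at Form 5, and list each eye's Form 3 to Form 5 change in microns.
- **SAP 7.5.5, missed visit:** state that an eye missing Form 4 is judged on its Form 3 to Form 5 change and flagged. The flag matters because a path such as 0, 12, 0 would still pass unseen.
- **Both documents:** use one name and one definition for the measured quantity.

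The cost is a few sentences and one listing, with no new visit or imaging. The downside is that the reported share of stable eyes may be lower. Under the assumed errors, a truly stable eye's chance of passing is unchanged at 99.9% for s = 2, falls from 86% to 82% for s = 4, and falls from 42% to 35% for s = 8.
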